
**Data Analysis Plan.** We will evaluate between-groups differences in peak magnitudes of responding during a single exposure to extinction using a 2x2 factorial, crossed, and randomized matched blocks design, employing batched randomization logic. First, we will calculate *observed* and *analytic* Pmax values (Gilroy et al., 2019) generated from logarithmically transformed PRFA outcomes to evaluate accuracy, reliability, and correspondence of Pmax estimates generated from PRA calculations (Reed et al., 2009). PRFA-PRA Pmax comparisons will be performed for each of the 160 PRA/PRFA assessments. Correspondences in Pmax will be assessed using Pearson correlations. Then, we will conduct a simple linear regression to assess relations between unit price and peak response magnitudes. Then, to evaluate (a) the effect of the timing of extinction (EO/AO) on peak response magnitude, (b) the effect of relative price (cheap/expensive) on response magnitude, and (c) price by timing interaction (whether the effect of timing on peak response magnitude changes depending on price) we will conduct a multiple linear regression analysis with price and timing as dummy coded categorical predictors. We will replicate this

analysis to evaluate collateral effects on *duration* of responding during extinction (a secondary analysis we anticipate will produce a less robust but potentially meaningful outcome).

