## 2.0 Rationale and Specific Aims

**Figure 3: Predictions**

**The Goal** of this application is to identify mechanisms responsible for bursts, and to facilitate strategic extensions toward discovery for treatments of challenging behavior. To accomplish this, we present two

related but distinct objectives. **Objective 1** entails identification of an efficient, accurate, and reliable assessment of  $P_{max}$ . **AIM 1: Evaluate correspondence between  $P_{max}$  values derived from assessments of varying efficiency. *H1: Progressive ratio (PR) reinforcer analysis (more efficient) will produce estimates which align with values obtained by progressive fixed-ratio reinforcer analysis (PFRA; less efficient).*** **Objective 2** entails determining the degree to which relative price and the timing of

extinction interact to increase or abate responding during extinction (thereby highlighting mechanisms of control). **AIM 2: Evaluate utility of manipulating baseline parameters for controlling bursts when variables are set according to demand and Pmax.** **H2:** Peak response magnitude during extinction will decrease as unit price increases. Further, *baseline will moderate bursts in one of three distinct ways*. **First**, only unit price, relative to Pmax, will influence peak-response magnitude. **Second**, only timing of extinction (i.e., proximity of baseline consumption to demand threshold) will influence peak-response magnitude. **Third**, unit price relative to Pmax, and consumption relative to demand, interact to influence peak-response magnitude during extinction.

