**Response Training.** Will entail a forced-choice exposure and 10 opportunities to independently earn reinforcers (1/response). If independence is not achieved, we will target different responses and reinforcers.

**Progressive Ratio Reinforcer Analysis (PRA).** Begins with free-access, followed by three PRAs interspersed with controls. Control will occur prior to PRA. To avoid satiation, only one PRA will be conducted per appointment. Thus, including free access, this assessment requires four appointments. **Free access.** Carefully measured units of the reinforcer will be delivered freely, independent of target responding. Participants will be informed they can consume (e.g., eat, listen to) reinforcers at will, and that reinforcers will be replaced (when relevant) as they are consumed. Sessions end when no reinforcers are consumed for one minute. **Control.** Facilitators will place the target-response apparatus in front of participants and indicate that responding will not result in reinforcement. Sessions end following 1 min without responding. **PRA.** Facilitators will indicate that responding results in reinforcement, but that more work will be required as time passes. Following every other reinforcer delivery, price will increase by three responses (i.e., FR1, FR4, FR7, etc.).

[figure not shown]
**Progressive Fixed-Ratio Reinforcer Analysis (PRFA).** Will be similar to PRA with a few exceptions. First, no control condition. Next, within-session schedules are fixed. That is, requirements increase by 3 across sessions, rather than across reinforcers (this allows us to establish demand at each schedule). To control for satiation, we’ll conduct one PRFA session per appointment (session ends following 1 min without responding; or after 1 hour). The assessment ends after aggregate responses for one session fall below those of previous sessions (thus avoiding premature exposure to extinction). During our pilot study, this assessment was completed in six or fewer appointments, each ranging from 5 to 27 min.

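### Aim 1 promises accuracy, reliability and alignment of PRA-derived Pmax, but the only statistic named, Pearson's r, would not detect a PRA that reads too high or too low for everyone

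*Combined protocol and SAP*

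**What the plan says.** Section 2.0 sets the target in three steps. Objective 1 is the "identification of an efficient, accurate, and reliable assessment of" Pmax. Aim 1 is to "Evaluate correspondence between" Pmax values from assessments of differing efficiency. H1 is that the PRA "will produce estimates which align with values obtained by progressive fixed-ratio reinforcer analysis".

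The Data Analysis Plan in Section 5.0 says that observed and analytic Pmax, "generated from logarithmically transformed PRFA outcomes", will be used "to evaluate accuracy, reliability, and correspondence of Pmax estimates generated from PRA calculations". (PRFA there is the same assessment as PFRA elsewhere.) It adds that "PRFA-PRA Pmax comparisons will be performed for each of the 160 PRA/PRFA assessments", and then names the statistic: "Correspondences in Pmax will be assessed using Pearson correlations".

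No mean difference, limits of agreement, concordance or intraclass coefficient, repeatability measure or margin for alignment appears anywhere in the document. Section 8.0 says of Aim 1 only that it is adequately powered.

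**The concern.** Whether one method can stand in for another is a question about level: does the quick assessment return the same number as the slow one, person by person? Pearson's r asks something else, namely whether the two sets of numbers lie near some straight line. A PRA that ranks participants well but reads high for all of them is neither accurate nor aligned, yet it can have a high r.

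What is at stake is the Aim 1 conclusion. With r as the only named summary and no criterion beside it, a PRA with a systematic error could be reported as corresponding with the PFRA, and H1 could be read as supported. The three PRA runs per participant would allow a direct estimate of repeatability, but no statistic is attached to them.

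**Working it through.** **What each promise is matched to**

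| Promise | Where | Statistic named |
|---|---|---|
| Correspondence | Aim 1; Data Analysis Plan | Pearson's r |
| Accuracy | Objective 1; Data Analysis Plan | none |
| Reliability | Objective 1; Data Analysis Plan | none (observer scoring aside; see the objection) |
| Alignment of PRA with PFRA | H1 | none, and no margin |

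The plan gives no figure for Aim 1 to reproduce. Its sample size of 77 belongs to the three-predictor regression of Aim 2. It does reproduce (omnibus F test, f² = 0.15, α = 0.05: power 0.802 at 77), but it says nothing about agreement.

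**Inputs for an illustration**

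- Price step: 3 responses (PRA and PFRA paragraphs, Section 5.0).
- Range of observed Pmax: pilot PFRAs took at most six appointments and end on a drop in responding. Starting at FR1, as in the pilot example, the schedules are FR1, 4, 7, 10, 13 and 16, so observed Pmax is at most about FR13.
- SD of Pmax: not given. An even spread over 1, 4, 7, 10, 13 has mean 7, variance (36 + 9 + 0 + 9 + 36)/5 = 18 and SD 4.24. Assumed range: 3 to 4.24, equal for both methods.
- SD of the paired differences: not given. Assumed 2 to 3.

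**Step 1. r without bias.** With equal SDs s and SD of differences D, r = 1 − D²/(2s²).

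**Step 2. Add a constant bias of one step.** Raw-scale r does not move. Lin's concordance is 2rs²/(2s² + 3²).

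| s | D | r, with or without bias | Concordance, no bias | Concordance, +3 |
|---|---|---|---|---|
| 3 | 2 | 1 − 4/18 = 0.78 | 0.78 | 0.778 × 18/27 = 0.52 |
| 3 | 3 | 1 − 9/18 = 0.50 | 0.50 | 0.500 × 18/27 = 0.33 |
| 4.24 | 2 | 1 − 4/36 = 0.89 | 0.89 | 0.889 × 36/45 = 0.71 |
| 4.24 | 3 | 1 − 9/36 = 0.75 | 0.75 | 0.750 × 36/45 = 0.60 |

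The no-scatter limiting case (D = 0) gives r = 1.00 with concordance 18/27 = 0.67 to 36/45 = 0.80. It shows the principle and is not a realistic data set.

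**Step 3. Does the log scale rescue r?** The plan logs the PFRA outcomes and does not state the scale of the correlation. Over FR1 to FR13, evenly spread and without scatter, the correlation of ln x with ln(x + 3) is 0.988, and with ln(x + 6) it is 0.978. A PRA that reads 1.5 times too high has r = 1.00 on both scales in the same setting. Its mean error is 0.5 × 7 = 3.5 responses, and raw concordance is 2 × 1.5 × 18/(18 + 40.5 + 3.5²) = 54/70.75 = 0.76.

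**Step 4. Is significance of r a useful bar?** With 80 pairs, |r| of 0.22 or more is significant at two-sided 0.05. That is weak evidence of alignment.

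**Step 5. Can the planned data answer the right question?** The half-width of the 95% CI for the mean difference is t·D/√n. With n = 80 and t = 1.990 it is 1.990 × 2/8.944 = 0.45 for D = 2, and 0.67 for D = 3. A bias of 3 responses would be clear. Each limit of agreement would be known to about ±0.38 D, that is ±0.76 to ±1.15 responses.

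**The case against.** The best defence is that Aim 1 speaks of correspondence, r is assigned to exactly that word, and the plan nowhere says that a high r confirms H1. Aligning can loosely mean moving together. The promised assessment-by-assessment comparisons might also bring an offset into view. This stands in part: that H1 would be declared supported is an inference about reporting, not a stated rule. It does not remove the gap, because the same sentence of the plan also promises accuracy, and the comparisons have no summary statistic or criterion.

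A second defence is that reliability is covered, since a second observer will collect reliability data in at least 30% of sessions (Dependent Variables paragraph, Section 5.0). That concerns whether two people score the same session alike. It does not concern whether a participant's three PRA runs agree, or whether PRA agrees with PFRA.

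Third, the numbers rest on assumptions, and this is fair. The FR13 ceiling assumes a start at FR1 with every appointment used for a ratio; it would be FR10 if one were spent on free access. It does not bound analytic Pmax. The invariance of r on the raw scale needs none of these assumptions.

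Two stronger readings are tempting and unsupported. A reader might infer that the PRA is biased; the documents give no evidence of that. A reader might also infer that the trial's main comparison is compromised. It is not: baseline schedules are built from PFRA Pmax and the PRA mean breakpoint (Extinction Challenge, Section 5.0), not from PRA Pmax.

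**Conclusion.** The point holds and is confined to Aim 1. The plan promises accuracy, reliability and alignment, and names only a measure of association. A constant bias on the raw scale, or a proportional bias on either scale, would leave that measure unchanged; a constant bias on the log scale would lower it only slightly. Under the assumed SDs, a one-step bias takes concordance from 0.50–0.89 to 0.33–0.71 while r stays at 0.50–0.89. These sizes are illustrative, because the documents report no distribution of Pmax.

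Two related matters are clarifications, not defects. The plan does not say what the 160 assessments count; 80 participants with two assessments each, hence 80 pairs, is the likeliest reading. Were 160 rows treated as independent pairs, the 95% CI for r = 0.80 would read 0.74 to 0.85 instead of 0.70 to 0.87 (Fisher z). Nor does it say how the "followed by three PRAs interspersed with controls" yield one PRA Pmax. The method cited for the PRA calculation may settle this, and averaging has a precedent in the plan's use of a mean breakpoint.

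**What to change.** In the Data Analysis Plan of Section 5.0:

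- Make the Aim 1 agreement analysis the paired PRA minus PFRA Pmax difference, or the ratio if the log scale is used. Use one pair per participant with both assessments, at most 80.
- Report the mean, 95% CI and 95% limits of agreement, for both observed and analytic PFRA Pmax. Percentile-based limits are optional.
- State in advance the difference that counts as aligned, on the scale analysed. The choice of scale matters: 3 responses is 75% at FR4 (3/4) but 23% at FR13 (3/13), and observed PFRA Pmax is resolved only to 3 responses.
- Report an ICC across the three PRA runs for reliability, named separately from observer reliability.
- Keep Pearson's r as descriptive.
- For clarity, say what 160 counts and how the three runs form one PRA Pmax.

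The cost is a little analysis work, a margin that needs a substantive justification, and an Aim 1 conclusion that may be less favourable than r alone would give. No new data and no more participants are needed.

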**Materials and Target Response.** For each participant, we will individualize and define (a) a target response with a corresponding apparatus, (b) a preferred edible item or sound manipulation ([name] et al., *in press*), and (c) a moderate- to low-preferred tangible item. All target responses will involve a two-step manipulation and restoration. The final step of each target response (i.e., restoration) will automatically set up another opportunity to complete the task (e.g., fold/unfold a hand towel).

**Dependent Variables, Procedural Fidelity, and Interobserver Reliability.** We will collect continuous timed-event measures of the frequency of target responding and reinforcer delivery, latency from session onset to delivery of programmed reinforcers, and overall session duration. Derivative measures appropriate to each analysis will serve as our dependent variables and will include breakpoint (i.e., the schedule of the last obtained reinforcer prior to response cessation [PRA]), demand (i.e., the number of reinforcers obtained prior to response cessation [PFRA]), Pmax (defined above [PRA & PFRA]), and peak response rate during extinction (Figure 1), depicted as a proportion of baseline (e.g., Figure 4). We will monitor fidelity, and a second trained observer will collect reliability data on all dependent variables across no fewer than 30% of sessions.

**General Appointment Protocol.** To minimize unintended coercive practice, all assessment-related activities will be framed as a choice. Specifically, facilitators will initiate appointments with a 5-min casual conversation. Prior to each session, facilitators will display the apparatus for target response and a low-preferred alternative activity and will say, “We are going to start a session, now. This just means I’m going to give you an opportunity to earn (reinforcer). During sessions I cannot talk to you. That’s just a rule I have to follow. It doesn’t mean I don’t want to talk or that I’m not happy. If you want (reinforcer) after the session starts, you can work on (target response). If you don’t want (reinforcer), or would rather talk to me, you only need to stop (target response) for one minute. You can also just say, ‘I’m done’. While you wait, you can (alternative activity) if you like.” All appointments will terminate the moment a participant indicates they would like it to end.

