### **Predicted relationship between timing, price, and response magnitude.**

EO relative to AO.

We predict that the mean magnitude of peak responding for participants assigned to cheap conditions will be higher than those assigned to expensive conditions, holding timing constant. Additionally, we predict the mean magnitude of peak responding will be higher for those participants assigned to EO as compared to AO, holding price constant. Further, we predict a timing by price interaction such that the difference in mean peak responding in cheap and expensive conditions will be bigger in

**Power Analysis.** Power analysis and sample size calculations were conducted using G\*power software. Since our study represents a novel contribution to the field, we cannot rely on previous literature to estimate the population value of R-squared or the appropriate effect size. However, our pilot data suggest the effect size will not be small. Thus, we calculated sample size based on a benchmark value for Cohen's  $f^2$  of 0.15 that corresponds to a medium effect size for R-squared (Cohen, 1988). To achieve 80% power in a regression model with three predictors and  $\alpha = .05$ , the number of required participants is 77. With a sample of 77, the power to find any one of the three predicted effects (given medium effect size) is 88. Since participants will be equally distributed across four groups, we budgeted time/effort for 80 participants. Under our most conservative study assumptions, AIMS 1 & 2 are adequately powered.

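### Cheap improvement to Aim 2: price and timing coefficients read straight from 0/1 coding are two-cell effects with a four-cell pooled standard error, so their 5% level depends on an unstated equal-variance assumption

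*Combined protocol and SAP*

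**What the plan says.** The Data Analysis Plan (section 5.0) evaluates timing, relative price and their interaction in one model: "we will conduct a multiple linear regression analysis with price and timing as dummy coded categorical predictors". The same analysis is repeated for duration of responding. The power paragraph confirms that the product term is in the model: "To achieve 80% power in a regression model with three predictors".

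The outcome, defined in section 5.0 under Dependent Variables, is "peak response rate during extinction (Figure 1), depicted as a proportion of baseline", a ratio that cannot be negative.

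The predictions are that the "mean magnitude of peak responding for participants assigned to cheap conditions will be higher than those assigned to expensive conditions", that "the mean magnitude of peak responding will be higher for those participants assigned to EO as compared to AO", and that the two factors interact.

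For this outcome the documents state no robust or unequal-variance standard error, no transformation and no check of residual variance. The only log transformation is applied to the demand data used for Pmax. They do not name the reference levels, and they do not say whether the price and timing effects will be read from the 0/1 coefficients or as effects averaged over the other factor. Participants are matched in tetrads, but the regression has no tetrad term.

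**The concern.** In a model with a product term and 0/1 coding, the price coefficient is the cheap-minus-expensive difference at the reference level of timing only. It uses two cells. Its ordinary standard error uses the residual variance of all four. If spread differs between EO and AO, that pooled variance does not fit the two cells being compared, and equal cell sizes do not repair it. The same holds for timing if spread differs between cheap and expensive.

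This bears on Aim 2 because section 2.0 sets out three rival patterns: only price matters, only timing matters, or they interact. If only timing matters and spread rises with the mean, the price test is the one that must hold 5%, and it is the one that is distorted. Whether it rejects too often or almost never depends on a reference level that the plan does not name.

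**Working it through.** **Inputs from the documents.** Three predictors, f² = 0.15, α = .05, 80% power, 77 required, 80 planned in four equal groups, hence 20 per cell.

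**Inputs assumed.** Two-sided tests; independent participants unless stated; SD ratio r between the two levels of the other factor of 1.25 to 2; CV of 30% to 80% where the ratio is linked to f².

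**1. The plan's own figure.** Noncentral F with 3 and N − 4 df and λ = 0.15N gives power of 80.2% at N = 77 and 81.9% at N = 80. The 77 reproduces, under one common residual variance.

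**2. Simple effect (0/1 coding).** Let the two cells compared have SD r and the other two SD 1.
- True variance: 2r²/20. Pooled variance: 2 × [(r² + 1)/2]/20.
- True-to-pooled SE ratio: √[2r²/(r² + 1)]. If the two cells compared are the less variable, it is √[2/(r² + 1)].
- At r = 2: √(4/2.5) = 1.265 and √(1/2.5) = 0.632.
- Normal approximation at r = 2 with critical value 1.99: 1.99/1.265 = 1.57, a two-sided error of about 11.5%.

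Simulated type I error (normal data, 20 per cell, pooled variance on 76 df):

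| SD ratio | SE ratios | Reference cells more variable | Reference cells less variable |
|---|---|---|---|
| 1.0 | 1.000 / 1.000 | 5.0% | 4.9% |
| 1.25 | 1.104 / 0.883 | 7.5% | 2.7% |
| 1.5 | 1.177 / 0.784 | 9.6% | 1.3% |
| 2.0 | 1.265 / 0.632 | 12.1% | 0.24% |

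A second simulation gave 7.4%/2.9%, 9.9%/1.3% and 12.5%/0.2% at ratios of 1.25, 1.5 and 2. Lognormal and gamma data at ratio 2 gave 11.6–12.2% and 0.27–0.53%. HC3 in the second simulation gave 4.7–5.1%.

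**3. Which ratio fits the plan's effect size?** If SD is proportional to the mean and only the other factor acts, f² = (r − 1)²/[2·CV²·(1 + r²)].
- CV 50%, r = 1.5: 0.25/(0.5 × 3.25) = 0.154, close to the plan's 0.15. Error is about 10% or 1.3%.
- CV 50%, r = 2: 1/(0.5 × 5) = 0.40, well above 0.15.
- At f² = 0.15, CV 30% implies r = 1.26 (7.6% or 2.5%), and CV 80% implies r = 1.97 (12.1% or 0.3%).

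**4. What is not affected.**
- Averaged price effect, equal cells: true variance (1/4)(Σσ²)/20; pooled variance [(Σσ²)/4]/20. These are the same. Simulated averaged main effects and interaction stayed at 4.6–5.3%.
- SD differing only by the factor tested (2, 1 against 2, 1): true variance (4 + 1)/20 = 0.25; pooled 2 × 2.5/20 = 0.25. Simulated 5.1%.

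**5. Matching.** With within-tetrad correlation ρ, the true SE of a two-cell difference is multiplied by √(1 − ρ), while the unblocked pooled SE hardly changes.
- r = 2, ρ = 0.2: 1.265 × 0.894 = 1.131; 1.99/1.131 = 1.76; about 8% (simulated 8.5%).
- r = 2, ρ = 0.3: 1.265 × 0.837 = 1.058; 1.99/1.058 = 1.88; about 6% (simulated 6.4%).
- HC3 without tetrad at ρ = 0.2: 1.99/0.894 = 2.23; about 3%. At ρ = 0.3: 1.99/0.837 = 2.38; about 2%.

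**The case against.** Four points count against the concern.

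- **No SDs are given.** That spread grows with the mean is a reasonable expectation for a ratio, but the documents do not show it. A reader might infer that the Aim 2 tests truly run at 12% or 0.3%. The documents do not support that: those rates need a 2:1 SD ratio, which at a CV of 50% means f² = 0.40 against the planned 0.15. This objection stands, so the rates can only be given as a range under assumptions.
- **The plan may intend averaged effects.** It asks for the effect of price and the effect of timing without saying how they are extracted. If they are averaged over the other factor, equal cells keep them near 5%. A reader might also infer that the interaction test is compromised; it is not. This stands and confines the point to coefficients read directly. It does not remove it, because 0/1 coding is the natural reading of the plan's words and software reports those coefficients by default.
- **Matching works the other way.** Positive correlation within tetrads makes the unblocked tests more conservative. At an assumed ρ of 0.3 and a ratio of 1.5, simulation gives 4.7%, so the inflation may vanish. This stands, and it also means that HC3 alone would not restore 5%.
- **Balance is planned.** This stands as a plan. Participants may stop at any time, however. In a simulation with assumed AO cells of 14 against 20, even averaged contrasts moved to 2.7–3.2%.

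**Conclusion.** The point holds as a cheap improvement, not as a demonstrated error in the plan. If the 0/1 price and timing coefficients are read as the effects, and the SD differs by the other factor by a ratio of 1.25 to 2, the true error of a nominal 5% test is about 7.5% to 12% or about 2.8% to 0.2%, depending on whether the reference cells are the more or the less variable. At the plan's f² of 0.15 with an assumed CV of 50%, it is about 10% or 1.3%. These figures rest on assumed SD ratios, 20 independent participants per cell and a reference level that the plan leaves open. Within-tetrad correlation would lower them all. With equal cells, the interaction and averaged main effects are not affected.

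**What to change.** In the Data Analysis Plan, for both the peak and the duration regressions:

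1. Use effect coding, test price and timing as main effects averaged over the other factor, and report simple effects as secondary.
2. Use HC3 standard errors.
3. Account for tetrad, because HC3 alone is conservative if matching induces correlation.

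How tetrad enters needs care. Twenty fixed tetrad intercepts plus three factorial terms give each participant a leverage of (20 + 3)/80 = 0.2875. HC3 then overstates the variance of an averaged contrast by about 1/(1 − 0.2875) = 1.40, and its SE by √1.40 = 1.18, so HC3 on top of tetrad dummies stays conservative. One form that copes with both unequal SDs and correlation is to compute each contrast within each complete tetrad and test the mean of the 20 values on 19 df. That would take the place of HC3 for those tests, at the price of fewer degrees of freedom and a need for complete tetrads.

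A log-ratio analysis limited to participants with a peak above zero is not a good substitute: it selects on an outcome observed after randomisation and may drop participants unequally across cells.

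The cost is a few sentences and a software option. Simulated power with HC3 falls from 94% to 93% for averaged contrasts. With price and timing each multiplying the ratio by 1.5 at a CV of 50%, power for the price simple effect at the EO reference (the more variable cells) falls from 78% to 67% with normal data, or from 81% to 71% with lognormal data; part of that loss is inflation removed. At the AO reference it rises from 49% to 70%.
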